### STATEMENT OF COMPLIANCE

The study will be conducted in compliance with this clinical study protocol, Good Clinical Practices (GCP) as outlined by International Council for Harmonization (ICH) of Technical Requirements for Pharmaceuticals for Human Use E6 (R2), and all applicable local and national regulatory requirements. Screening at any clinical study site may not begin prior to Ethics Committee (EC) or Institutional Review Board (IRB) approval.

Any amendments to the protocol or changes to the consent document will be approved before implementation of that amendment, unless allowed by regulatory guidelines (e.g., when necessary to eliminate immediate hazard to the participants). Reconsent of previously enrolled participants may be necessary depending on the nature of the amendment.

The principal investigator will ensure that changes to the study plan as defined by this protocol will not be made without prior agreement from the Sponsor and documented approval from the IRB of record, unless such a change is necessary to eliminate an immediate hazard to the study participants.

All personnel involved in the conduct of this study have completed Human Subjects Protection and GCP Training as outlined by their governing institution.

### LIST OF ABBREVIATIONS

Abbreviation	Definition
ACE2	Angiotensin converting enzyme 2
ADAM17	ADAM Metallopeptidase Domain 17
AE	Adverse event
ALP	Alkaline phosphatase
ALT	Alanine aminotransferase
AMP	Amplifier
ANGII	Angiotensin II
aPTT	Partial thromboplastin
AR	Adverse reaction
ARDS	Acute respiratory distress syndrome
AST	Aspartate aminotransferase
AT1R	Angiotensin II receptor type 1 receptor
BID	Twice daily
BL	Baseline
BMI	Body mass index
BP	Blood pressure
BUN	Blood urea nitrogen
CATB/L	Cathepsin B and L
CBC	Complete blood count
CCR	Chemokine receptor
C max	Maximum observed serum concentration
CoV	Coronavirus
COVID-19	Coronavirus disease 2019
CPE	Cytopathic effects
CRF	Case report form
CRO	Contract research organization
CRP	C-reactive protein
CTCAE	Common Terminology Criteria for Adverse Events
CYP	Cytochrome P450
DAIDS	Division of AIDS
DIC	Disseminated intravascular coagulation
DG	Dose group
DLT	Dose limiting toxicity
DMC	Data Monitoring Committee
DNA	Deoxyribonucleic acid
EC	Ethics Committee
ECMO	Extracorporeal membrane oxygenation
EC 50	Half maximal effective concentration
eCRF	Electronic case report form
EDC	Electronic data capture
EOS	End of study

Abbreviation	Definition
ЕОТ	End of treatment
FIO 2	Fraction of inspired oxygen
GCP	Good Clinical Practices
GI	Gastrointestinal
GRAS	Generally recognized as safe
GU	Genitourinary
НРМС	Hydroxypropylmethylcellulose
HR	Heart rate
IB	Investigator's Brochure
IC 50	Half maximal inhibitory concentration
IC 100	Total inhibitory concentration
ICF	Informed consent form
ICH	International Council for Harmonization
ICU	Intensive care unit
IEC	Independent ethics committee
IL	Interleukin
IL-6	Interleukin-6
IND	Investigational New Drug
INR	International normalized ratio
IRB	Institutional Review Board
IV	Intravenous
JAK	Janus kinase
LDH	Lactate dehydrogenase
LRTI	Lower respiratory tract infection
LTFU	Long-term follow-up
Mabs	Monoclonal antibodies
MERS-CoV	Middle East respiratory syndrome coronavirus
MODS	Multiple organ dysfunction syndrome
N	Sample size
NDA	New Drug Application
NEWS2	National Early Warning Score 2
NF-kB	Nuclear factor kappa-light-chain-enhancer of activated B cells
NIPVV	Noninvasive positive pressure ventilation
NG	Nasogastric
NP	Nasopharyngeal
OG	Orogastric
PaO 2	Partial pressure of oxygen
PD	Pharmacodynamics
PEG	Percutaneous endoscopic gastrostomy
PK	Pharmacokinetics
PK/PD	Pharmacokinetic/Pharmacodynamic
PO	By mouth
PRRs	Pattern-recognition receptors

Abbreviation	Definition
PTT	Prothrombin time
RR	Respiratory rate
RT-PCR	Reverse transcriptase polymerase chain reaction
RTSM	Randomization and Trial Supply Management
SAE	Serious adverse event
SAP	Statistical analysis plan
SAR	Suspected adverse reaction
SARS-CoV	Severe acute respiratory syndrome coronavirus
SARS-CoV-2	Severe acute respiratory syndrome coronavirus 2
SD	Standard deviation
SOC	Standard-of-care
SOE	Schedule of events
SOFA	Sequential Organ Failure Assessment
SpO 2	Peripheral capillary oxygen saturation
STAT	Signal transducers and activators of transcription
STAT3	Signal transducer and activator of transcription 3
SUSAR	Suspected unexpected serious adverse reaction
T2D	Type 2 diabetes
TEAE	Treatment-emergent adverse event
TF	Tissue factor
TID	Thrice daily
t max	Time at which C max is observed
TMPRSS2	Transmembrane serine protease 2
TNF-α	Tumor necrosis factor alpha
WBC	White blood cell
WHO	World Health Organization

### 1 SYNOPSIS

Title	A Phase 2/3 Randomized and Placebo-Controlled Study of ANA001 in the Treatment of Moderate and Severe COVID-19 Patients
Phase	2/3
Study Design	This is a randomized, double blind, placebo-controlled multicenter study to investigate the safety and efficacy of ANA001 in the treatment of subjects with moderate and severe coronavirus disease 2019 (COVID-19). A total of 436 subjects who meet all eligibility criteria at Screening will be randomized to be treated with ANA001 1,000 mg twice daily (BID) or matching placebo administered orally (PO). Randomization will be stratified by oxygenation (SpO 2 >93 and <98% on room air versus SpO 2 $\leq$ 93% on room air), diarrhea (presence/absence), and age ( $<$ 65/ $\geq$ 65). Each subject will be treated for 7 consecutive days. Additionally, every subject will be followed up for safety and efficacy up to day 60 (+2 days) after first dose.
	The study consists of 2 parts:
	Study Part 1: It includes 60 subjects randomized in 1:1 ratio to receive ANA001 or matching placebo to assess the safety and tolerability of ANA001 1,000 mg BID for 7 days. An independent Data Monitoring Committee will review the safety profile of ANA001 1,000 mg PO BID prior to the initiation of Part 2 of the study.  Study Part 2: It includes 376 subjects randomized in 1:1 ratio to receive ANA001 or matching placebo to demonstrate the statistical superiority of ANA001 1,000 mg PO BID for 7 days compared with matching placebo in the treatment of
	subjects with moderate and severe COVID-19. Additionally, the safety profile of ANA001 will be assessed compared with placebo.
Rationale	Niclosamide has demonstrated both antiviral and immunomodulatory activity with possible beneficial downstream effects on coagulation abnormalities observed in COVID-19. These effects support the development of ANA001, an oral formulation of niclosamide, for the treatment of COVID-19.  Hypothesis: ANA001 will reduce viral load and inflammation associated with cytokine dysregulation, acute respiratory distress syndrome (ARDS), and
	coagulation abnormalities and thus improve time to clinical improvement defined as hospital discharge recorded using the WHO Ordinal Scale for Clinical Improvement (Appendix 1).
Target Population	Patients with moderate and severe COVID-19 who fulfill the study entry criteria
Number of Participants	Total: Approximately 436 participants
	Part 1 (60 participants): 30 ANA001 + 30 matching placebo
T /	Part 2 (approximately 376 participants): 188 ANA001 + 188 matching placebo
Intervention	ANA001 1,000 mg PO BID or matching placebo for 7 days (i.e., 14 scheduled doses comprised of 56 capsules in total): All participants will also receive unrestricted access to standard-of-care as defined by the respective study sites.
Primary Objective and	Objective:
Primary Endpoints/Parameters	To evaluate the safety and tolerability of ANA001 as therapy for moderate
(Part 1)	and severe COVID-19 patients Endpoints/Parameters:
(- ··- v *)	Treatment-emergent adverse events (TEAEs), treatment-emergent serious
	adverse events (SAEs), deaths, and discontinuations due to a TEAE
	Vital signs and laboratory (hematology, chemistry, and coagulation) parameters
Secondary Objectives and Secondary Endpoints (Part 1)	Objectives:  • To evaluate the efficacy of ANA001 as therapy in moderate and severe COVID-19 patients

### To evaluate the PK of ANA001 **Endpoints:** Median time (in hours) to hospital discharge (where discharge is defined as a score of 1 or 2 in the WHO Ordinal Scale for Clinical Improvement Plasma concentrations of ANA001 will be explored on Day 1, 2, 3, or Day 4 **Exploratory Objectives and** Objectives: **Exploratory Endpoints** To evaluate clinical improvement using National Early Warning (Part 1) Score 2 (NEWS2) To evaluate the need and duration of rescue therapy To evaluate the effect on subjective symptoms of COVID-19 To evaluate progression of COVID-19 from moderate or severe to more severe (i.e., moderate to severe, moderate to critical, or severe to critical) To evaluate the effect of ANA001 on requirement for oxygen and/or assisted ventilation To evaluate time to resolution of the WHO Ordinal Scale for Clinical Improvement To evaluate the effect of ANA001 on thromboembolic events To evaluate the relationship of ANA001 and markers of inflammation associated with acute respiratory distress syndrome (ARDS) To evaluate the relationship between ANA001 plasma concentrations and viral dynamics **Endpoints:** Mean change from baseline (BL) in NEWS2 on Day 15 Mean number of days on rescue treatment (COVID-19 therapies that are FDA approved or have emergency-use authorization) within 15 days after enrollment Median time (in days) to resolution of subjective symptoms assessed by the Investigator to be potentially due to COVID-19 including: fever, cough (productive or non-productive), sore throat, malaise, headache, muscle pain, gastrointestinal symptoms (i.e., nausea, vomiting, or diarrhea), shortness of breath (with or without exertion), and respiratory distress Proportion of participants who's COVID-19 progresses to Severe or Critical (Appendix 4) within 15 days after enrollment Proportion of participants requiring ICU admission within 15 days after enrollment Mean change from baseline (BL) in SOFA score on Day 8 and Day Proportion of participants requiring supplemental O2, high-flow nasal cannula (HFNC) oxygen, noninvasive positive pressure ventilation (NIPPV) or mechanical ventilation on Day 8 and Day 15 Mean number of days on mechanical ventilation within 15 days after enrollment Mean number of oxygenation-free days within 15 days after enrollment Proportion of participants who achieve a score of 1 in the WHO Ordinal Scale for Clinical Improvement (Appendix 1) on Day 8 and Day 15. Median time (in hours) to a 2-point improvement in the WHO Ordinal

enrollment

Scale for Clinical Improvement

Incidence and severity of thromboembolic events within 15 days after

	Incidence of abnormal markers of inflammation (CRP, IL-6, TF, MCP-1, and IP-10) on Day 8
	• Mean change in viral load from baseline (BL) on Days 1, 4, 8, 15, and 28
	Mean time (in days) to viral load undetectable by nasopharyngeal (NP) swab
Primary Objectives and	Objectives:
Primary Endpoints (Part 2)	To evaluate the efficacy of ANA001 as therapy in moderate and severe COVID-19 patients
	To evaluate the safety and tolerability of ANA001 as therapy for moderate and severe COVID-19 patients
	Endpoints/Parameters:
	• Time to clinical improvement as measured by median time (in hours) to hospital discharge (where discharge is defined as a score of 1 or 2 in the WHO Ordinal Scale for Clinical Improvement)
	TEAEs, treatment-emergent SAEs, deaths, and discontinuations due to a TEAE
	Vital signs and laboratory (hematology, chemistry, and coagulation) parameters
Secondary Objectives and	Objectives:
Secondary Endpoints	To evaluate clinical improvement using NEWS2
(Part 2)	To evaluate the need and duration of rescue therapy
	Endpoints:
	Mean change from baseline (BL) in NEWS2 on Day 15
	Mean number of days on rescue treatment (COVID-19 therapies that are FDA approved or have emergency-use authorization) within 15 days after enrollment
Exploratory Objectives and	Objectives:
Exploratory Endpoints (Part 2)	To evaluate the effect on subjective symptoms of COVID-19
	To evaluate progression of COVID-19 from moderate or severe to more severe (i.e., moderate to severe, moderate to critical, or severe to critical)
	To evaluate the effect of ANA001 on requirement for oxygen and/or assisted ventilation
	To evaluate time to resolution of the WHO Ordinal Scale for Clinical Improvement
	To evaluate the effect of ANA001 on thromboembolic events
	To evaluate the relationship of ANA001 and markers of inflammation associated with acute respiratory distress syndrome (ARDS)
	To evaluate the relationship between ANA001 and viral dynamics
	Endpoints:
	Median time (in days) to resolution of subjective symptoms assessed by the Investigator to be potentially due to COVID-19 including: fever, cough (productive or non-productive), sore throat, malaise, headache, muscle pain, gastrointestinal symptoms (i.e., nausea, vomiting, or diarrhea), shortness of breath (with or without exertion), and respiratory distress
	Proportion of participants who's COVID-19 progresses to Severe or Critical (Appendix 4) within 15 days after enrollment
	Proportion of participants requiring ICU admission within 15 days after enrollment

Mean change from baseline (BL) in SOFA score on Day 8 and Day 15

[figure not shown]
	Proportion of participants requiring supplemental O 2 , high-flow nasal
	cannula (HFNC) oxygen, noninvasive positive pressure ventilation (NIPPV) or mechanical ventilation on Day 8 and Day 15
	Mean number of days on mechanical ventilation within 15 days after enrollment
	Mean number of oxygenation-free days within 15 days after enrollment
	• Proportion of participants who achieve a score of 1 in the WHO Ordinal Scale for Clinical Improvement (Appendix 1) on Day 8 and Day 15.
	Median time (in hours) to a 2-point improvement in the WHO Ordinal Scale for Clinical Improvement
	Incidence and severity of thromboembolic events within 15 days after enrollment
	• Incidence of abnormal markers of inflammation (CRP, IL-6, TF, MCP-1, and IP-10) on Day 8
	• Mean change in viral load from baseline (BL) on Days 1, 4, 8, 15, and 28
	Mean time (in days) to viral load undetectable by nasopharyngeal (NP) swab
Number of Sites	Approximately 20 study sites in the United States
Participant Duration	Treatment Duration: 7 consecutive days (defined as 14 doses administered BID)
	Total study duration (including screening period through the end of study visit): Approximately 60 (+2) days
Study Duration	The study will last approximately 1.5 years.
Inclusion Criteria	To be included in this study, an individual must satisfy all the following criteria:
	
 
Willing and able to provide written informed consent (or their legally authorized representative) prior to performing study procedures. If necessary, emergency consent may be obtained per local procedures.
 
Hospitalized.
 
Understands and agrees to comply with planned study procedures, including ability and willingness to swallow multiple small capsules.
 
Male or female adult ≥18 years of age at the time of informed consent.
 
Positive for SARS-CoV-2 by a standard RT-PCR assay or alternative Sponsor approved assay within 7 days of randomization and no more than 36 hours after hospitalization.
 
Presence of symptoms of lower respiratory tract infection (LRTI) including at least 1 of the following: fever, cough, sore throat, malaise, headache, muscle pain, or more significant lower respiratory tract symptoms, including shortness of breath (at rest or with exertion).
 
At least 1 of the following: respiratory rate (RR) ≥20 breaths per minute, room air SpO2 <98%, requirement for supplemental oxygen, heart rate (HR) ≥90 beats per minute, or temperature >38.3°C.
 
Access to a telemedicine platform for outpatient visits in cases where visits to the study site are not possible (e.g., telephone, smartphone, tablet, or computer).
 
Women of childbearing potential must agree to abstinence from heterosexual intercourse or use at least 1 form of contraception not including hormonal contraception from the day of screening through Day 30.
 

Exclusion Criteria	If an individual meets any of the following criteria at screening, he or she is ineligible for this study:
	
 
Hospitalized, but no longer requires ongoing inpatient medical care (i.e., hospital discharge is anticipated in ≤24 hours.
 
Per the clinical judgment of the Investigator, the patient is not anticipated to survive >48 hours OR is under palliative care.
 

- 3. Evidence of critical illness, defined by at least 1 of the following:
  - Respiratory failure requiring at least 1 of the following:
    - a. Endotracheal intubation and mechanical ventilation, oxygen delivered by high flow nasal cannula (heated, humidified, oxygen delivered via reinforced nasal cannula at flow rates >20 L/min with fraction of delivered oxygen >0.5)
    - b. Noninvasive positive pressure ventilation (NIPPV), OR
    - c. Extracorporeal membrane oxygenation (ECMO) or clinical diagnosis of respiratory failure (i.e., clinical need for 1 of the preceding therapies, but preceding therapies not able to be administered in setting of resource limitation)
  - Shock (defined by systolic blood pressure (BP) <90 mm Hg, or diastolic BP <60 mm Hg or requiring vasopressors), OR

  - Multi-organ dysfunction/failure
- Severe CNS conditions, e.g., acute stroke, severe confusion, or other acute mental status changes that may significantly determine duration of hospitalization and patient outcomes.
- 5. Chronic kidney disease requiring dialysis.
- Anticipated transfer to another facility, which is not a study site, within 72 hours.
- 7. Known allergy to the study drug or salicylate containing medications.
- 8. Suspected and/or confirmed pregnancy or breastfeeding.
- 9. Current or planned participation in any other interventional clinical trial under a US IND or EUA.
- 10. Patients receiving chemotherapeutic agents and/or immunomodulators (including glucocorticoids, monoclonal antibodies (Mabs), or plasma transfusions) for chronic disease conditions (e.g., malignancies, rheumatoid arthritis or other autoimmune diseases).

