#### 9.6 **Handling of Missing Data**

Missing efficacy assessments will be imputed using a multiple imputation method appropriate to the pattern of missingness. Details of the considered patterns and associated sensitivity analyses will be described in the Statistical Analysis Plan.

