7.5 Efficacy Analysis for Exploratory Endpoints

As a general strategy, analyses of the exploratory efficacy endpoints will be presented for all participants in the Full Analysis Set.

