7.5.5 ICU Admission

The number and proportion of participants requiring ICU admission at any time within the first 15 days after enrollment will be tabulated by treatment group and Baseline WHO Ordinal Scale for Clinical Improvement score. The corresponding 95% binomial confidence interval will also be reported. Sample size permitting, Wilson's method will be used to derive these confidence intervals. The difference in proportions will also be reported with the corresponding 95% confidence interval using Newcombe's method. Should the number of observed admissions be small, the exact distribution will be used instead of the normal approximation to derive the confidence intervals.

Participants who did not get admitted to ICU will not contribute to this analysis

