7.5.7 Oxygen and Assisted Ventilation

Number and proportion of participants requiring each of the following on Days 8 and 15 will be tabulated by treatment group:

- Supplemental oxygen only: This is defined as nasal cannula and oxygen level 1-15 L/min or FiO2≤35%, or simple facemask, or non-rebreather
- High-flow nasal cannula (HFNC) oxygen: This is defined as nasal cannula and oxygen level>15L/min or FiO2>40% and up to 100%.
- Noninvasive positive pressure ventilation (NIPPV): This is defined as non-invasive CPAP or non-invasive - BIPAP
 Mechanical ventilation: This is defined as invasive – mechanical PPV, invasive – negative pressure, or invasive ECMO

Each proportion will be analyzed in a way similar to the analysis of proportion of participants requiring ICU Admission in Section 7.5.5. Additionally, the proportion of subjects requiring any of the above will also be analyzed.

Mean number of days on mechanical ventilation within 15 days after enrollment and mean number of oxygenation-free days within 15 days after enrollment will be tabulated by treatment group. Participants who are not off mechanical ventilation are censored at date of completion/withdrawal. Participants without requiring oxygenation within 15 days after enrollment are censored at Day 15 or date of completion/withdrawal, whichever is earlier.

Sample size permitting, these endpoints will be compared in a way similar to the analysis of the Duration of COVID-19 Symptoms in Section 7.5.3.

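### SAP 7.5.7 has no rule for deaths in the Day 8 and Day 15 respiratory-support proportions, so excess mortality can appear as respiratory benefit

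*Protocol*

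**What the plan says.** The protocol lists the endpoint for Part 1 as "Proportion of participants requiring supplemental O2, high-flow nasal cannula (HFNC) oxygen, noninvasive positive pressure ventilation (NIPPV) or mechanical ventilation on Day 8" and Day 15, and repeats it for Part 2 (Synopsis; Tables 2 and 3). It is exploratory in both parts.

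- **SAP 7.5.7** implements it: "Number and proportion of participants requiring each of the following on Days 8 and 15 will be tabulated by treatment group". The four levels are supplemental oxygen only, HFNC, NIPPV and mechanical ventilation, and the proportion needing any of them is also analysed. There is no death category and no rule for deaths. On method: "Each proportion will be analyzed in a way similar to the analysis of proportion of participants requiring ICU Admission in Section 7.5.5".
- **SAP 7.5** sets the population: "analyses of the exploratory efficacy endpoints will be presented for all participants in the Full Analysis Set". SAP 5.1 defines that set as all randomized participants.
- **SAP 7.5.5** covers participants "requiring ICU admission at any time within the first 15 days after enrollment", with Wilson and Newcombe intervals. Its closing sentence says that those never admitted to the ICU do not enter the analysis.
- **Missing data.** SAP 8 applies no visit windows and analyses visits as reported. SAP 10.1 plans only limited, unspecified imputation for exploratory endpoints. Protocol 9.6 is broader: "Missing efficacy assessments will be imputed using a multiple imputation method appropriate to the pattern of missingness". None of the three mentions death.
- **Death elsewhere.** The one explicit death rule for an efficacy endpoint is the censoring rule for time to discharge in SAP 7.4. Protocol Appendix 1 scores death as 8 on the WHO scale, but 7.5.7 does not use that score.

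**The concern.** A participant who died on Day 5 uses no oxygen or ventilator on Day 8. Unless a rule says otherwise, the worst outcome is grouped with the best. The arm with more early deaths then has fewer people left to be on support, and the difference in proportions, with its Newcombe interval, can lean towards that arm. The outcome of such a participant is known, so this is a question of endpoint definition and not of missing data.

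The results could also carry some weight. Protocol 4.1 has the DMC review efficacy as well as safety after Part 1 enrolment, with futility among the possible outcomes. Protocol 6.6.2 lets the sponsor change the Part 2 sample size or endpoints in the light of Part 1 efficacy data.

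**Working it through.** The documents state no figure for these proportions, so there is none to reproduce. The sample sizes come from the protocol (30 per arm in Part 1, 188 per arm in Part 2) and the interval method from SAP 7.5.5. All death and support rates below are assumptions.

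**1. Where a death goes under each available reading**

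- Literal reading (Full Analysis Set, status on the day): in the denominator, in no numerator.
- Reported visits only: dropped, leaving a survivors-only comparison.
- Imputation: given an imputed support status for a day on which the participant was not alive.

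None of these counts death itself as unfavourable.

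**2. Direction, with no treatment effect on support among survivors**

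Let s be the proportion of survivors on support (equal in both arms) and d the proportion dead.

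- Literal proportion: s(1 - d). Difference, ANA001 minus placebo: -s(dA - dP).
- Dead or on support: s(1 - d) + d. Difference: (1 - s)(dA - dP).

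| Deaths, ANA001 v placebo | s | Literal | Death as failure |
|---|---|---|---|
| 5% v 5% | 20% to 40% | 0 | 0 |
| 10% v 5% | 20% | -0.20 × 5 = -1.0 | 0.80 × 5 = +4.0 |
| 10% v 5% | 40% | -0.40 × 5 = -2.0 | 0.60 × 5 = +3.0 |
| 15% v 5%, or 20% v 10% | 20% | -0.20 × 10 = -2.0 | 0.80 × 10 = +8.0 |
| 15% v 5%, or 20% v 10% | 40% | -0.40 × 10 = -4.0 | 0.60 × 10 = +6.0 |

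Differences are in percentage points. The two rules have opposite signs whenever mortality differs. A survivors-only analysis gives 0 in every row, which hides the deaths.

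**3. When the deaths occur among those on support**

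Part 2 size: 63 of 188 per arm need support, and 19 of these die on ANA001 and 9 on placebo before the assessment day. That leaves 63 - 19 = 44 and 63 - 9 = 54 on support, and 188 - 19 = 169 and 188 - 9 = 179 survivors.

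The Newcombe limits combine the Wilson limits (l, u) of each arm: d - √[(p1 - l1)² + (u2 - p2)²] and d + √[(u1 - p1)² + (p2 - l2)²].

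For the literal rule:

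- ANA001: 44/188 = 23.40% (Wilson 17.92 to 29.95).
- Placebo: 54/188 = 28.72% (Wilson 22.73 to 35.57).
- Lower limit: -5.32 - √(5.48² + 6.85²) = -14.1.
- Upper limit: -5.32 + √(6.55² + 5.99²) = 3.6.

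| Rule | ANA001 | Placebo | Difference (95% CI), points |
|---|---|---|---|
| Literal | 44/188 | 54/188 | -5.3 (-14.1 to 3.6) |
| Survivors only | 44/169 | 54/179 | -4.1 (-13.4 to 5.3) |
| Death as failure | 63/188 | 63/188 | 0.0 (-9.5 to 9.5) |

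Part 1 size: 10 of 30 per arm need support, and 4 v 1 of these die.

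| Rule | ANA001 | Placebo | Difference (95% CI), points |
|---|---|---|---|
| Literal | 6/30 | 9/30 | -10.0 (-30.7 to 11.8) |
| Survivors only | 6/26 | 9/29 | -8.0 (-29.8 to 15.5) |
| Death as failure | 10/30 | 10/30 | 0.0 (-22.8 to 22.8) |

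Here dropping the deaths does not remove the apparent benefit.

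**4. ICU admission**

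The measure is cumulative, so a participant admitted to the ICU who later dies is already an event. Only a death without ICU admission could be scored as a non-event. The closing sentence of 7.5.5 raises a separate problem: if those not admitted are left out, numerator and denominator are the same people and the proportion is 100% in both arms. That cannot be the intent, yet 7.5.7 borrows its method from this section without fixing its own denominator.

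**The case against.** A reader might infer that the plan actively counts deaths as not needing support. It does not say so. The rule is absent, and SAP 8, SAP 10.1 and protocol 9.6 leave other readings open. This objection stands, and the point is therefore about a missing rule. It does not rescue the analysis, because none of those readings counts death as unfavourable.

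A reader might also infer that ICU admission suffers in the same way. It does so only for deaths without ICU admission.

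Starker counts could be used to claim a statistically significant false benefit. With 36 v 19 dead and 30 v 47 on support out of 188 per arm, the literal difference is -9.0 points (95% CI -17.1 to -0.9). Nothing in the documents supports those rates, and protocol 5.4 excludes critical illness and patients not expected to survive beyond 48 hours. Survivors only, the same counts give 30/152 v 47/169, or -8.1 points (-17.2 to 1.3). The milder examples above also have intervals that include zero.

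Finally, excess deaths would not be hidden. Deaths are a primary safety endpoint in both parts, SAP 7.6.1 tabulates adverse events leading to death, and the DMC sees unblinded data. The endpoints are outside the testing hierarchy of protocol 9.7, and protocol 9.3 plans no formal inference for Part 1. All of this stands and limits the consequence. It does not make the respiratory table itself correct.

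**Conclusion.** The gap is real and modest. SAP 7.5.7 does not say how deaths on or before Day 8 or Day 15 enter the support proportions, and no reading available from the documents treats death as unfavourable. If mortality differs between arms, the literal reading biases the difference towards the arm with more deaths, and its sign can be opposite to that of dead or requiring support. With equal mortality and equal support use among survivors there is no bias.

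Under the milder assumed rates the distortion is a few percentage points, and no larger figure can be defended from the documents. The denominator conflict in SAP 7.5.5 is a plain inconsistency that needs no assumption, and it may carry over to 7.5.7. The available SAP covers Part 1 only, so what the Part 2 SAP will say is unknown. The priority is low to moderate.

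**What to change.** In SAP 7.5.7, and in the Part 2 SAP:

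- State that the denominator is all Full Analysis Set participants.
- Define the any-support proportion as dead or requiring support on the day.
- Show death as its own row beside the four support levels.
- State that support status is not imputed after death.

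In SAP 7.5.5:

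- Delete or reconcile the sentence that leaves out participants not admitted to the ICU.
- Report ICU admission or death within 15 days alongside ICU admission.

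The cost is a few sentences and one extra table row. No new data are needed, because deaths and the WHO score are already collected. The drawback is that the composite mixes death with need for support; the separate death row lets the reader see which of the two drives a difference.
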